Study Protocol and Statistical Analysis Plan

Clinicaltrials.gov ID: NCT05178979

Unique Protocol ID: K01MH121663-01A1

Secondary IDs: 1K01MH121663-01A1 [U.S. NIH Grant/Contract Award Number]

Title: A Gender Transformative Implementation Strategy With Providers to

Improve HIV Outcomes in Uganda

Protocol date: 11 July 2023 (final version date of approved IRB protocol)

Pls: [name]

Contact PI: [name], BC, [contact]

Contents

Inclusion criteria	3
Recruitment & Sampling	3
Data collection	4
Questionnaires	4
Process Data	5
Data management	6
Qualitative data	6
Quantitative data	6
Data safety monitoring plan	7
Adverse events	7
Training of the RAs/Facilitators	8
Training of research assistants	8
Training of intervention facilitators	8
Statistical Analysis Plan	9

Inclusion criteria

Provider cohort for training intervention, assessment, and exit focus groups (intervention trial). We will recruit providers for participation in our intervention trial for the provider training from the two selected clinics. The goal is to recruit the entire population of providers at each of the two clinics, which is approximately 20-35 providers per clinic (Luwero Hospital, Mityana Hospital, Kalagala HCIV and Namayumba HCIV) for participation. This cohort will include all HIV care providers at the 4 selected clinics, including: medical officers, clinical officers, HIV nurses, midwife, linkage facilitators, and counselors. These participants will be 18 years of age or older and fluent in English or Luganda.

Patient cohort assessment (intervention trial). In addition to the assessment of the cohort of ~80-140 HIV providers, we will obtain additional data on the impact of the provider training on patient outcomes including quality of care, patient satisfaction, clinic attendance, ART adherence, and viral load (from patient clinic records) by assessing 240 (60 per treatment facility, gender balanced) purposively sampled patients at baseline, 6-, and 12-month follow-up.

Eligibility includes:

- 1. HIV-infected;
- 2. enrolled in care at the clinic of recruitment;
- 3. pre-ART (newly diagnosed) or newly initiated on ART (within 1 year) or struggling with treatment adherence, defined in two ways:
 - a. most recent viral load results unsuppressed as assessed through clinic records

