 - or self-reported non-adherence as by the Adult AIDS Clinical Trials Group (AACTG) scale 4-day adherence recall questions. This scale has demonstrated good construct validity in Uganda and strong correlations with viral load;
- 4. 18 years of age or an emancipated minor;
- 5. fluent in Luganda or English.

Recruitment & Sampling

Provider cohort for training intervention, assessment, and exit focus groups (intervention trial). Once research staff are trained and our two clinics have been randomly assigned as intervention or control arm, we will recruit providers for participation in our intervention trial for the provider training. The goal is to recruit the entire population of providers at each of the four clinics, which is approximately 20-35 providers per clinic (Luwero Hospital, Mityana Hospital, Kalagala HCIV, and Namayumba HCIV) for participation; approximately 35 at each hospital and 25 at each HCIV (total: 80-140). With support from Mildmay Uganda (see Letter of Support), we will generate support for the training first in the broader Health Districts (with medical superintendents and District Health Officers) through in-person meetings and garnering their feedback on the intervention through invitations to serve on/make recommendations for a "Training Steering Committee." After District support is attained, we will then conduct facility mobilization with an inperson presentation of the goals research study at each of the four clinics. Eligibility for providers includes being an HIV care provider at one of the four selected clinics. After the larger facility

mobilization meeting, the research assistant will meet one-on-one with HIV providers to individually inform them of the study, allow them to ask any questions in a private space, and obtain written informed consent. Though we aim to recruit all HIV providers at each clinic for participation, any provider can decline to participate. The informed consent process will include consent for both participation in the provider training, baseline, 6- and 12-month assessments, and an exit focus group. To mask the randomization of intervention and control, we will consent participants for participation in all aspects of the training.

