Patient cohort assessment (intervention trial). In addition to the assessment of the cohort of ~140 HIV providers, we will obtain additional data on the impact of the provider training on patient outcomes including quality of care, patient satisfaction, clinic attendance, ART adherence, and viral load (from patient clinic records) by assessing 240 (60 per clinic, gender balanced) purposively sampled patients at baseline, 6- and 12-month follow-up. Patients will be non-randomly approached when presenting to care by a Research Assistant based on a review of clinic records. After being referred by a clinician, our research assistant will inform individuals of the study and assess eligibility using an eligibility screening tool. No identifying information will be recorded during the eligibility screening. If eligibility is met and the patient would like to participate, the research assistant will obtain written informed consent and collect patients' contact information (for follow-up reminders) and conduct the baseline questionnaire in the clinic or another agreed upon location.

Data collection Questionnaires

For the provider cohorts randomized to the Intervention clinics, the chronological activities include: enrollment; baseline interview immediately after enrollment; participation in ~21 hours of intervention content; follow-up assessments at 6-months and 12-months follow-up; one exit focus group post-intervention. Each data collection activity and its duration is detailed below:

- Baseline provider assessment (for all provider participants). After the informed consent process a one-on-one interview (~25 minutes) using a computerized structured questionnaire in the clinic or another agreed upon location will be conducted with providers at both clinics. The questionnaire will collect demographic information and measures to assess provider outcomes. The total duration of participation for the baseline survey is approximately 25 minutes.

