- 6-, and 12-, month follow-up provider assessments (all provider participants). Research Assistants will conduct the 2 follow up interviews using an individual structured interviewer-administered computer-based interview in the clinic or another agreed upon location for patient and providers. Providers have the option to complete these assessments over the telephone only if they have transferred to working at another clinic and cannot be reached in person. The follow-up questionnaires will serve as a measure of intervention effects on provider's gender equitable attitudes and gender awareness and other related constructs (see Measures). This questionnaire is approximately 25 minutes per time point. Across the 2 assessments, the total duration for survey participation is approximately 50 minutes.

For the patient cohort (n=240) enrolled in the intervention and control clinics. To assess the effect of the provider training on patient-level outcomes, we will assess change overtime in patient outcomes in a cohort of HIV patients enrolled at the 2 clinics. These patients do not receive any intervention, but will participate in an assessment across 3 time-points (following the same schedule as the provider assessment). They will also agree to a review and data extraction of health information from of their HIV clinic records at each time point.

- Baseline patient assessment (all patient participants). HIV patients referred to the study and interested in participating will first answer a brief set of questions to assess enrollment. No data will be recorded at this time. If eligible and interested, we will obtain written informed consent before continuing with the baseline questionnaire. Using a computerized structured questionnaire, a research assistant will conduct the survey in the clinic or another agreed upon location at both clinics. The questionnaire will collect demographic information and measures to assess patient outcomes related to HIV care engagement (e.g., clinic attendance, medication adherence, patient satisfaction). Data will also be extracted at this time and directly entered into the computerized survey from patient clinic records (e.g., treatment regiment, CD4 count, viral load). Total duration of baseline interview is approximately 60 minutes.

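### The randomisation sentence counts two clinics, but the named sites and cohort totals fit only four, and the SAP never gives the number of clusters

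*Combined protocol and SAP*

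**What the plan says.** The clinic count takes two values in the protocol's operative text.

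**Two clinics**
- Inclusion criteria, provider cohort: providers come from two selected clinics, and the aim is to "recruit the entire population of providers at each of the two clinics".
- Recruitment & Sampling, provider cohort: "our two clinics have been randomly assigned as intervention or control arm". No other sentence describes the random assignment.
- Data collection, Questionnaires: the patient cohort is "a cohort of HIV patients enrolled at the 2 clinics". The baseline provider, baseline patient and follow-up patient assessments each refer to both clinics.

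**Four clinics**
- Inclusion criteria, provider cohort, same paragraph: four sites are named (two hospitals and two HCIVs), and the cohort covers "all HIV care providers at the 4 selected clinics".
- Recruitment & Sampling, provider cohort, directly after the randomisation sentence: the aim is to "recruit the entire population of providers at each of the four clinics", with the same four sites named. Facility mobilisation and provider eligibility also refer to four clinics.

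**Totals**
- Patients are assessed "by assessing 240 (60 per clinic, gender balanced) purposively sampled patients" (Recruitment & Sampling, patient cohort). Inclusion criteria gives the same figures per facility.
- Providers number 20-35 per clinic and 80-140 in total, with about 35 per hospital and 25 per HCIV. The patient paragraph of Recruitment & Sampling puts the provider cohort at about 140.

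The Statistical Analysis Plan uses GEE to account for clinic clusters and repeated measures. It gives neither the number of clusters nor their allocation to arms.

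**The concern.** Training is assigned to whole clinics, so the number of clinics is the sample size at the level where the arms were randomised. It determines how much information there is on between-clinic variation, and hence what the clustering adjustment can achieve. A wrong count elsewhere would be a matter for copy-editing. Here it stands in the one sentence that defines the randomisation, and the SAP offers no second statement to check it against. A reader cannot establish from the text how many units were randomised or how many fell in each arm, and so cannot judge the standard errors that the GEE will produce.

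**Working it through.** **Inputs.** 60 patients per clinic and 240 in total; 20-35 providers per clinic and 80-140 in total; about 35 providers per hospital and 25 per HCIV; two hospitals and two HCIVs named. All are in Inclusion criteria or Recruitment & Sampling. The documents give no power calculation, intracluster correlation or target effect, so there is no sample-size formula to reproduce.

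**Step 1: reproduce the stated totals.** Total = number of clinics × number per clinic.

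| Clinics | Patients | Providers |
|---|---|---|
| 4 | 4 × 60 = 240 (matches) | 4 × 20 = 80 to 4 × 35 = 140 (matches) |
| 2 | 2 × 60 = 120 (half) | 2 × 20 = 40 to 2 × 35 = 70 (half) |

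The Questionnaires section sets 240 patients beside two clinics. That would need 240 / 2 = 120 per clinic, against the stated 60.

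**Step 2: check by facility type.** Any two of the named sites give at most 35 + 35 = 70 providers (two hospitals); one of each type gives 35 + 25 = 60, and two HCIVs give 50. None reaches the stated lower limit of 80. All four give 2 × 35 + 2 × 25 = 120. That lies within 80-140 but is 20 below the figure of about 140 in the patient paragraph (20 / 140 = 14%).

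**Step 3: look for indirect evidence of the count.** The Questionnaires section refers to intervention clinics in the plural, and Process Data samples focus groups from each of the intervention health centres, again in the plural. Process Data also plans about 8 exit groups of 6-8 trained providers, that is 8 × 6 = 48 to 8 × 8 = 64 people, subject to saturation, and the schedule of activities gives each provider one group. One clinic has at most 35 providers; two have 40-70. More than one intervention site is incompatible with two clinics in two arms.

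**Step 4: what the count means for inference.** Between-clinic degrees of freedom are the number of clinics minus the two arms.
- Two clinics, one per arm: 2 − 2 = 0.
- Four clinics, if two per arm: 4 − 2 = 2, with t(0.975, 2 df) = 4.30. There are 6 ways to choose two clinics from four, so the smallest two-sided permutation p-value is 2/6 = 0.33.

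Step 4 needs no assumed correlation or outcome rate.

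**The case against.** The strongest reply is that the answer is already in the text. The sentence straight after the randomisation sentence says four and names the sites, and both cohort totals agree with four exactly. On that view the two-clinic phrases are leftovers from an earlier design, and the remedy is editorial. Much of this stands. Leftover wording is the likeliest explanation, although the documents do not say so. The SAP is written in the past tense, so rewording cannot change the design that was run.

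The reply does not dispose of the point. The count is wrong in the sentence that defines the randomisation, and the SAP does not supply the right one.

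Three stronger readings are tempting, and the documents do not support them:
- A reader might infer one clinic per arm, with training and clinic fully confounded and a design that cannot answer its question. The four named sites, the totals and the plural references to intervention sites all tell against this. The randomisation sentence itself does not say one clinic to each arm.
- A reader might infer that the cohort sizes fit neither count. Both fit four exactly and fail only with two.
- A reader might want to put a standard error on the difference between two and four clinics. That needs an intracluster correlation and an outcome rate that the documents do not give. A formula for one time point would also not match the planned time-by-arm interaction.

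**Conclusion.** The point holds as an internal contradiction in the number of randomised units. Two-clinic wording appears in seven places, including the randomisation sentence. The named sites and the totals (240 patients, 80-140 providers) fit only four; two clinics would give half of each. That four clinics were randomised is an inference from those figures, strong but still to be confirmed. Two per arm is a weaker inference, because no section states the split. The figures of 2 degrees of freedom and t = 4.30 are conditional on it.

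Correcting the count does not remove the limitation of having four clusters; it makes that limitation visible. A smaller mismatch remains in the provider total, 120 by facility type against about 140. The correction should be made, because readers should not have to infer the number of randomised units.

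**What to change.** 1. Correct the two-clinic wording to four in all seven places: twice in Inclusion criteria (provider cohort), once in the randomisation sentence of Recruitment & Sampling, and four times under Questionnaires (baseline provider, patient cohort introduction, baseline patient, follow-up patient).
2. In the randomisation sentence, state from the allocation record how many clinics were randomised and how they were split between arms. Do not assume two per arm.
3. In the SAP, state the number of clusters in total and per arm, and base between-clinic inference on that number. If the record shows two per arm, this means 2 between-clinic degrees of freedom and a critical t of 4.30.
4. Reconcile the provider total: 2 × 35 + 2 × 25 = 120, the range 80-140, and the figure of about 140.

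**Cost.** Items 1, 2 and 4 are text corrections plus one look at the allocation record. They change no data, participants or procedures. Item 3 has a real price: precision that reflects four clusters will be less favourable, and that should be accepted and reported.

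### Patients enter through clinician referral with no rule for who is referred, and nothing requires enrolment and baseline to finish before allocation is known, so the patient time-by-arm effect can be biased

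*Combined protocol and SAP*

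**What the plan says.** Under Recruitment & Sampling, the patient cohort is 240 purposively sampled patients, 60 per clinic and balanced by gender. On the approach: "Patients will be non-randomly approached when presenting to care by a Research Assistant based on a review of clinic records". On the step to screening: "After being referred by a clinician, our research assistant will inform individuals of the study and assess eligibility". How the records review and the referral fit together is not explained.

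The eligibility list under Inclusion criteria admits two kinds of patient. One is new to treatment (pre-ART, or within a year of starting). The other has adherence problems, shown by an unsuppressed viral load or by "self-reported non-adherence as by the Adult AIDS Clinical Trials Group (AACTG) scale 4-day adherence recall questions".

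On the provider side, Inclusion criteria states: "This cohort will include all HIV care providers at the 4 selected clinics". Recruitment & Sampling gives the order: "Once research staff are trained and our two clinics have been randomly assigned as intervention or control arm, we will recruit providers". The one statement on masking concerns provider consent: "To mask the randomization of intervention and control, we will consent participants for participation in all aspects of the training".

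Under Questionnaires, providers in intervention clinics are enrolled, interviewed at baseline and then given about 21 hours of training. The patient cohort is said to follow the provider assessment schedule, with follow-up at 6 and 12 months after each patient's own baseline.

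The SAP reports the time-by-arm interaction from GEE. Variables that differ between arms at p < 0.10 are tried as covariates. No covariate-by-time term is mentioned.

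**The concern.** When clinics are randomised and patients are recruited afterwards, randomisation does not protect the patient comparison unless selection is independent of allocation. Here the person who opens the door to screening is a clinician. Since the provider cohort is meant to include every HIV care provider at the clinics, that clinician is probably a trial participant. This is an inference; the documents do not say it. Eligibility, the quota and gender balance limit who may enter, but not which eligible patients are put forward.

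If clinicians or research assistants know the allocation while patients are still being enrolled, referral may come to depend on it. If enrolment runs into the training period, some intervention patients have a baseline that training has already touched. Because follow-up is counted from each patient's own baseline, late enrolment would not show in the visit timing. At stake is the patient-level time-by-arm effect on care quality, satisfaction, attendance, adherence and viral load. The provider outcomes are not affected.

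**Working it through.** **The plan's own figure.** 4 clinics × 60 = 240 reproduces the patient cohort; 2 × 60 = 120 does not, although some sections speak of two clinics. A two-versus-two split, hence 120 patients per arm, is my assumption. The documents give no effect size, SD, correlation, intraclass correlation (ICC) or accrual rate, so every input below is assumed.

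**What cancels and what does not.** Let Y0 = S + e0 and Y1 = S + e1, with total variance 1, var(S) = ρ and no training effect. Selection creates a baseline gap g between arms. Take g = 0.1 to 0.3 SD and ρ = 0.3 to 0.7.

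| Nature of the gap | Gap at follow-up | Time-by-arm contrast | Baseline-adjusted contrast |
|---|---|---|---|
| Stable level | g | 0 | (1−ρ)g = 0.03 to 0.21 |
| Selection on the observed baseline value | ρg | −(1−ρ)g = −0.03 to −0.21 | 0 |
| Wholly transient | 0 | −g = −0.10 to −0.30 | −ρg = −0.03 to −0.21 |

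At g = 0.3 and ρ = 0.3, 0.5, 0.7, selection on the observed value gives −0.21, −0.15, −0.09 in the planned contrast; simulation agrees. The planned contrast is safe only in the first row. A baseline-adjusted model is safe only in the second, so changing to it would not settle the matter.

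For scale, the SE of the change contrast is √(2(1−ρ) × 2/120) = 0.153, 0.129, 0.100, so the 95% half-width is 0.30, 0.25, 0.20 SD ignoring clustering. With an assumed ICC of 0.01 to 0.05 and 60 per clinic, the design effect 1 + 59 × ICC is 1.59 to 3.95. The half-width then runs from 0.20 × √1.59 = 0.25 to 0.30 × √3.95 = 0.60 SD.

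**Case mix.** Spurious effect = (arm difference in the share of a patient type) × (difference in 12-month change between types). Shares 10 to 20 points apart and changes 20 to 40 points apart give 0.1 × 0.2 = 2 points up to 0.2 × 0.4 = 8 points. In a linear model a main-effect covariate shifts all visits alike and leaves this unchanged; a case-mix-by-visit term brings it to about 0. For the odds ratios that the SAP uses for binary outcomes the figure would differ.

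**Late baseline.** If a share f of intervention patients enrol after training starts and a share k of the effect is already present, 1 − fk is retained. With f = 0.1 to 0.5 and k = 0.5 to 1, that is 0.95 down to 0.50.

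**Referral habits unrelated to allocation.** With a between-clinic SD of 10 points in case-mix share and two clinics per arm, the arm difference has mean 0 and SD 0.10 × √(1/2 + 1/2) = 10 points. That is chance imbalance from having few clinics, not bias.

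**The case against.** The strongest reply is on timing. The provider sequence is given as chronological, with baseline before training, and patients follow the same schedule. Read together, the plan intends a pre-training patient baseline. The stated purpose of the uniform consent is to mask allocation, and if patients are enrolled on schedule that masking could cover the referral period too. This largely stands: the late-baseline route needs a departure from the schedule. What the text lacks is a clinic-level requirement that the last patient baseline precede disclosure and training. The masking sentence concerns provider consent and does not say how long masking lasts.

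Second, referral may be no more than an introduction to patients already listed from the records, and purposive sampling is a declared choice. The text allows that reading but does not settle it, and either way no order of approach is given.

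Third, patient outcomes are introduced as additional data, and their rank as primary or secondary is not stated. This limits the weight of the point.

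Two stronger readings are tempting. A reader might infer that patients are enrolled by people who know the allocation, or after training has begun; the documents do not say so, and the schedule points the other way. A reader might also see a contradiction between recording no data at screening (Baseline patient assessment) and "No identifying information will be recorded during the eligibility screening". There is none, since recording nothing includes recording nothing identifying.

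**Conclusion.** The point holds as a conditional one. Patient selection is discretionary, no referral order is set, and completion of enrolment and baseline before disclosure and training is implied rather than required. If referral depends on allocation, or enrolment overlaps training, the patient time-by-arm effect can be biased. The documents do not support saying that it is biased, and direction and size cannot be determined from them.

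A stable level difference cancels. A case mix with a different time course, selection on a momentary value, or a late baseline does not. That newly treated patients and patients with adherence problems change differently over 12 months is a reasonable expectation, not a figure from the plan. The illustrated sizes rest wholly on assumed inputs. Except for the clustered half-width, they ignore clustering, and allowing for it makes the biases smaller relative to the trial's uncertainty. Confidence is medium. This is a cheap improvement.

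**What to change.** **If enrolment has not begun:**

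- At every clinic the research assistant approaches consecutive presenting patients within gender, using the records review and the screening tool, until 30 men and 30 women are enrolled. Clinicians may introduce the study but do not select. This removes discretionary selection; it does not balance case mix between clinics.
- State that patient enrolment and baseline at each clinic are complete before allocation is disclosed to its clinicians and research assistants, and before training starts.
- Keep a de-identified screening tally per clinic (sex, criterion met, numbers approached, eligible and consented), and amend the Baseline patient assessment text, which now has nothing recorded at screening, to allow it.

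The cost is protocol wording, some list work and a possible delay to training, which cannot be sized without an accrual rate.

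**If enrolment is complete**, as the past tense of the SAP suggests:

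- Tabulate patient enrolment dates against allocation disclosure and training start, by clinic.
- Tabulate case mix by arm and clinic: viral load status, self-reported adherence and, if recorded, ART duration. ART start date is not among the examples of extracted data, so it may need a further records check or be left out.
- Keep the planned model as the main analysis. Add one sensitivity analysis with case-mix-by-visit terms regardless of p-value, omitting a variable when it is itself the outcome. Add another restricted to patients with a pre-training baseline, with the cut-off date for control clinics defined beforehand.
- State the limitation for patient outcomes.

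The cost is analysis time and the retrieval of dates. These analyses address measured case mix and timing only; they cannot show who was never referred.

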To evaluate the time by intervention effect on primary and secondary outcomes, we used Generalized Estimating Equations (GEE) in SPSS v. 28, which can account for dependency in the data related to the clinic clusters and repeated measures. First, we used GEE to examine baseline equivalence between treatment arms in both HIV care provider and client cohorts. We tested variables that differed at a level of p < 0.10 between treatment arms as covariates in the models testing intervention effect; only variables significant at p < 0.05 and/or making a difference in the intervention effect were maintained in the final models. We report the time by arm interaction. For all provider and client analyses, we tested the time by intervention by gender effect. For providers, we also tested the time by intervention by cadre effect, categorizing providers into certified health workers (licensed doctors, nurses, counselors) vs. lay health workers or non-specialized staff (e.g., peers). These interactions are only presented if they were statistically significant (p < 0.05). We report unstandardized betas (b) and standard errors (SE) for continuous outcomes and odds ratios (ORs) and adjusted odds ratios (AORs) and 95% confidence intervals (CIs) for binary outcomes.

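### The plan does not identify its primary outcome or time point, describes no multiplicity handling, and shows gender and cadre interactions only when they are significant

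*Combined protocol and SAP*

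**What the plan says.** The Statistical Analysis Plan is one paragraph. It uses generalized estimating equations "To evaluate the time by intervention effect on primary and secondary outcomes" and adds "We report the time by arm interaction". It covers two cohorts, since it first examines "baseline equivalence between treatment arms in both HIV care provider and client cohorts". It tests a three-way interaction with gender for every provider and client analysis, and one with cadre for providers, and displays these only when p < 0.05. Binary outcomes are reported with odds ratios and 95% confidence intervals, continuous outcomes with a coefficient and standard error.

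The outcomes are named elsewhere. The patient cohort paragraphs under Inclusion criteria and under Recruitment & Sampling list "quality of care, patient satisfaction, clinic attendance, ART adherence, and viral load". The provider follow-up item under Data collection, Questionnaires, names "gender equitable attitudes and gender awareness and other related constructs" and refers the reader to a Measures section, which the document's contents list does not include. The schedule for providers in intervention clinics gives "follow-up assessments at 6-months and 12-months follow-up", and patients follow the same schedule.

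No section assigns an outcome or a visit to the primary or the secondary class. None gives a significance level for the main tests, a testing order or an adjustment.

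**The concern.** The same test is applied to an unranked set of outcomes in two cohorts. With no named primary outcome or visit, any one significant result could be put forward as the trial's finding, and a reader could not tell a confirmatory result from a selected one. The display rule for interactions adds a second route to selection. A gender or cadre effect that reaches p < 0.05 by chance is shown, while the null results that would put it in context are not. What is at stake is how much weight a claim that the training worked can bear.

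**Working it through.** The plan states no familywise error rate, power or significance level for the main tests, so there is no figure of its own to reproduce.

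**Inputs**
- Patient outcomes: 5, listed under Inclusion criteria.
- Provider outcomes: 2 named, plus an uncounted group of related constructs (Questionnaires). The total of 5 + 2 = 7 is therefore a minimum.
- Follow-up visits: 2. The main tests number 7 if time-by-arm is one joint test per outcome, or 7 × 2 = 14 if each visit is tested.
- Significance level: assumed two-sided 0.05. The plan attaches 0.05 only to keeping covariates and to displaying interactions; its 95% intervals for binary outcomes are consistent with the assumption.
- Each test is assumed to hold its nominal level.

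**Independent tests**, chance of at least one false positive = 1 − 0.95^m:
- Provider cohort alone, m = 2: 1 − 0.9025 = 9.8%
- Patient cohort alone, m = 5: 1 − 0.7738 = 22.6%
- Both cohorts, m = 7: 1 − 0.6983 = 30.2%
- Both cohorts, visits tested separately, m = 14: 1 − 0.4877 = 51.2%

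**Correlated tests.** The documents give no correlations, so a range was simulated: 200,000 draws of normal test statistics, 5 patient and 2 provider outcomes, with the cohorts independent of each other.

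| Correlation between outcomes | 7 tests | 14 tests, visit correlation 0 | 14 tests, 0.5 | 14 tests, 0.7 |
|---|---|---|---|---|
| 0 | 30.2% | 51.3% | 48.4% | 45.7% |
| 0.3 | 28.4% | 48.6% | 46.0% | 43.0% |
| 0.5 | 25.7% | 44.8% | 42.5% | 39.4% |
| 0.7 | 21.9% | 39.2% | 36.6% | 34.0% |

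Seven tests therefore give about 22% to 30%, and fourteen about 34% to 51%. Passing one half takes more than ln 0.5 / ln 0.95 = 13.5 independent tests, that is, at least 14.

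**Favourable direction only.** A two-sided 0.05 test errs in favour of the training 2.5% of the time:
- m = 7: 1 − 0.975^7 = 16.2%
- m = 14: 1 − 0.975^14 = 29.8%

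**Interactions, kept separate.** At least 7 gender tests and 2 cadre tests are planned. With one test each at 0.05 and no true interaction, 9 × 0.05 = 0.45 would be expected to meet the display rule by chance. These tests concern effect modification, so they are not added to the error rate for the main effect.

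**The case against.** The strongest reply is that the plan does have a primary and secondary split, because it says so. The designation may sit in the Measures section or in the registration, neither of which is available here. That stands. A reader might infer that the trial has no primary outcome, but the documents support only that this document does not identify one.

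A reader might also infer that the plan sets an unadjusted 0.05 for every main test. It does not. No level is stated for those tests, and 0.05 is a working assumption.

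A third tempting inference is that a chance positive is more likely than not. The figures do not show this. Seven tests give at most 30%, and fourteen pass one half only if all are independent, which is implausible for two visits by the same people. The singular wording about the interaction also fits one joint test per outcome at least as well as separate visit tests.

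Pooling the cohorts can be challenged too. Providers and patients are different people answering different questions, and taken separately the figures are 9.8% and 22.6%. That is fair, and adjusting across the two cohorts is one option rather than a requirement. Finally, a claim of benefit needs a result in the favourable direction, which brings the seven-test figure down to 16%.

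None of this supplies the missing designation or justifies showing only significant interactions.

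**Conclusion.** The point holds as an omission of identification and control, together with a selective display rule. Under an assumed two-sided 0.05, the chance of at least one false positive among the seven named outcomes is roughly four to six times the nominal 5% (21.9 / 5 = 4.4; 30.2 / 5 = 6.0). The upper limit for separate visit tests is 51%. Within cohorts the inflation is smaller for providers (9.8%) than for patients (22.6%).

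These figures depend on assumed correlations, on counting only the named outcomes, and on each test keeping its nominal level, which generalized estimating equations with four clinics do not guarantee. The documents do not support a claim that a chance result will probably carry the conclusion. Nor do they favour a particular outcome, or 12 months over 6 months, as primary.

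Because the analysis paragraph is in the past tense, a primary outcome named only now could itself be chosen after the results were known.

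**What to change.** 1. For each cohort, state the primary outcome and time point that were prespecified, as registered, with evidence that the choice predates the analysis.
2. State the significance level and sidedness, and whether time-by-arm is one joint test or a contrast at each visit.
3. If a cohort has more than one primary, adjust within that cohort, for example by Holm.
4. Label all other outcomes and visits secondary. Report them with estimates and 95% confidence intervals, for continuous as well as binary outcomes, and make no confirmatory claim from them.
5. Drop the rule that shows interactions only when significant, and report every planned gender and cadre interaction whatever its p value.
6. If no designation predates the analysis, label all results unadjusted and exploratory.

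The cost is analysis plan wording and longer tables, and fewer results can be called confirmatory.
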